If a subject experiences a DLT during the DLT observation period, the subject will discontinue treatment. However, any subject(s) tolerating the dose level through the DLT observation period will continue to receive the same dose of study drugs even if a dose de-escalation occurs for other study subjects.

A Dose Level Review Committee (DLRC) will evaluate the safety data from each cohort of the Phase 1b. Members of this committee will include participating investigators or designees as well as the Sponsor (at a minimum: the Medical Monitor or designee, a Drug Safety representative and a Biostatistician).

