### **5.3. Definition of Dose-Limiting Toxicity (DLT)**

The assessment of DLT will follow the guidelines provided in the [CTCAE v 4.03](#). A DLT is defined as any Grade 3 or higher non-hematologic or Grade 4 hematologic AE possibly related to study drug(s) occurring during the DLT observation period with the following clarifications for the toxicities below:

- Grade 4 vomiting or Grade 3 nausea and vomiting despite maximum medical supportive care and persisting >3 days
- Grade 3 or 4 diarrhea despite maximum medical supportive care and persisting >7 days
- Grade 3 fatigue persisting >7 days
- Grade 3 neutropenia lasting >7 days or with fever
- Grade 3 infusion reaction that does NOT resolve with appropriate clinical management

During the Phase 1b DLT observation period, subjects will be replaced for any of the following reasons:

- Missed >4 consecutive doses or missed 7 total doses of ibrutinib.
- Missed dose of MEDI4736 or received the MEDI4736 dose outside of the protocol-allowed window ( $\pm 2$  days).

- Study drug discontinuation for any reason other than DLT (ie, including PD).

Subjects who are replaced for missed doses may continue to receive study treatment if there is a clinical benefit and will be followed for response assessment and overall survival, but they will not be part of the DLT analysis.

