#### **10.4.1. Phase 1b**

Dose de-escalation will follow the 6+3 design described in [Section 5.2](#) and up to 4 cohorts including 3 dose de-escalation cohorts (1, -1A, -1B, and -2) will be enrolled if needed to determine the RP2D for the combination therapy.

A total of 6-36 subjects eligible for DLT assessment will be enrolled into Phase 1b of the study with 6-9 DLT-evaluable subjects (regardless of tumor type) per dose cohort. Up to 4 dose cohorts will be tested. Subjects are considered DLT-evaluable if they receive the assigned dose of study treatment (both ibrutinib and MEDI4736) and complete the safety follow-up through the DLT-observation period.

Cohorts -1A and -1B are two parallel dose de-escalation cohorts. Subjects will be enrolled concurrently in the sequence of -1A followed by -1B. For example, the first available subject goes to -1A, the second to -1B, the third to -1A, the fourth to -1B, etc. However, when one dose de-escalation cohort needs an additional 3 subjects to evaluate DLTs, all available subjects will

be assigned to this cohort first. If necessary, the dose de-escalation cohort -2 will be enrolled thereafter.

Subjects in Phase 1b who were dosed at the RP2D and with a tumor type as defined for Phase 2 may also be included in the Phase 2 analysis.

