1.1. Study Design

This is a non-randomized, open-label, multi-center, Phase 1b/2 study to evaluate the efficacy and safety of ibrutinib in combination with durvalumab in subjects with relapsed or refractory solid tumor types (Stage III/IV per TNM staging):

- Non-small Cell Lung cancer (NSCLC): adenocarcinoma or squamous-cell carcinoma
- Breast cancer: HER2 positive or triple negative
- Pancreatic cancer: adenocarcinoma

RECIST 1.1 criteria will be used to evaluate response and document objective disease progression.

Phase 1b:

Phase 1b will follow a 6+3 dose de-escalation design to evaluate dose limiting toxicity (DLT) and determine the recommended phase 2 dose (RP2D) or maximum tolerated dose (MTD) for this study. In cohort 1 (consisting of 6 subjects regardless of tumor type), ibrutinib will be administered PO at a dose of 560 mg daily in combination with durvalumab at a dose of 10 mg/kg IV every 2 weeks in 28-day cycles until DLT or disease progression occurs. The DLT observation period includes Cycle 1 and laboratory assessments on Day 1 of Cycle 2 which will occur before the durvalumab infusion on Day 1 of Cycle 2. If 2 subjects within the initial cohort of 6 subjects experience a DLT, an additional 3 subjects will be enrolled at the same dose level. If 3 or more of 6 subjects experience a DLT, dose de-escalation will occur. If the subject incidence of DLTs during the first 28 days (Cycle 1=28 days and including laboratory assessments on Day 1 Cycle 2) of study treatment is <33.3% (ie, ≤ 1 of 6 or ≤ 2 of 9), this dose level will be considered safe to proceed to Phase 2, and will be defined as the RP2D. A DLT is defined as any Grade 3 or higher non-hematologic or Grade 4 hematologic AE possibly related to study treatment(s) occurring during the DLT observation period.

A similar 6+3 cohort design will be utilized in the dose de-escalation cohorts (see Table 1). De-escalation cohorts -1A and -1B will be opened simultaneously to determine which dosing schedule is most appropriate for the phase 2 portion of the study. Determination of the RP2D will be based on the safety profile of the 2 treatment regimens. If necessary, the dose de-escalation cohort -2 will be enrolled thereafter.

Table 1: Phase 1b Dosing Levels

28-Day Dosing Cycle	Ibrutinib	MEDI4736
Cohort 1	560 mg once daily PO	10 mg/kg IV
Cohort -1A*	420 mg once daily PO	10 mg/kg IV
Cohort -1B*	560 mg once daily PO	3 mg/kg IV
Cohort -2	420 mg once daily PO	3 mg/kg IV

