2.1. Analysis Sets

Enrolled Population

This population includes all subjects who were enrolled in Phase 1b and Phase 2 (signed the informed consent and met all eligibility criteria).

Response-evaluable Population

The Response-evaluable Population is defined as all enrolled subjects who received at least one dose of study treatment (ibrutinib or durvalumab) and provided at least one post-baseline response assessment. This population includes all the qualified subjects from both Phase 1b and Phase 2. The Response-evaluable Population will be used as the primary population for analyses based on overall response rate and disease control rate at Week 20 (end of Cycle 5).

Safety Population (Treated Population)

Safety population (Treated Population) includes all subjects who received at least 1 dose of study treatment (ibrutinib or durvalumab). Subjects in this population will be analyzed as randomized for the randomized subjects. The safety population will be used to summarize the safety (including dosing) data.

DLT Evaluable Population for Phase 1b

DLT evaluable population includes Phase 1b subjects who received study treatment and did not meet the criteria for subject replacement (in Section 1.4.1) during the DLT observation period.

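### Neither the SAP nor the protocol states that a subject with a DLT is always DLT-evaluable, so some DLTs can be replaced out of the Phase 1b count

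*SAP*

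**What the plan says.** **Analysis set.** SAP 2.1 defines the DLT-evaluable population as Phase 1b subjects who received study treatment and "did not meet the criteria for subject replacement (in Section 1.4.1) during the DLT observation period". It has no clause that keeps a subject who had a DLT. SAP 1.4, as supplied, covers sample size and has no subsection 1.4.1.

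**Replacement criteria.** Protocol 5.3 gives three reasons, any one of which is enough:

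1. "Missed >4 consecutive doses or missed 7 total doses of ibrutinib"
2. "Missed dose of MEDI4736 or received the MEDI4736 dose outside of the protocol-allowed window" (two days either side)
3. "Study drug discontinuation for any reason other than DLT (ie, including PD")

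Only the third mentions DLTs. Section 5.3 adds that subjects replaced for missed doses are left out of the DLT analysis.

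**Second definition.** Protocol 10.4.1 calls a subject DLT-evaluable if the assigned dose was received and the subject is able to "complete the safety follow-up through the DLT-observation period". Again there is no exception for a subject who had a DLT.

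**Action on a DLT.** Protocol 5.2: "If a subject experiences a DLT during the DLT observation period, the subject will discontinue treatment".

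**Decision rule.** Protocol 5.2 and SAP 1.1 accept a dose at no more than 1 DLT in 6 subjects or 2 in 9.

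**The concern.** The recommended Phase 2 dose (or MTD) is a Phase 1b primary endpoint, and it sets the dose for about 130 subjects in the Phase 2 analyses, 6 to 9 of whom come from Phase 1b. The decision rests on 6 to 9 subjects per cohort, so one or two DLTs decide the outcome.

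A subject with toxicity is the subject most likely to miss doses. If missed doses lead to replacement with no exception for DLTs, removal from the analysis depends on the outcome being counted. The error runs one way: a lost DLT is replaced by a fresh subject who may have none, and the observed rate falls.

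**Working it through.** **The plan's own figures.** 1/6 = 16.7% and 2/9 = 22.2%, both below 33.3%. 2/6 and 3/9 equal 33.3% and fail. One cohort of 6 gives 6 subjects and four cohorts of 9 give 36, matching the stated 6 to 36.

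**Can the wording remove a real DLT?** There are three routes.

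- *DLTs that need time to qualify.* Under Protocol 5.3, Grade 3 or 4 diarrhea is a DLT only once it has persisted for more than 7 days, so on day 8 of the event at the earliest. More than 4 consecutive missed doses means 5. If ibrutinib is withheld from event day h, the fifth miss falls on event day h + 4, which is before day 8 whenever h is 3 or less. Protocol 5.5.1.4 and Table 2 withhold ibrutinib for persistent Grade 3 or 4 diarrhea. The toxicity table in 5.5.2.4 permanently discontinues the study drug or regimen for it. A stop before day 8 is not yet a stop for a DLT, so even the third bullet could replace the subject. Grade 3 fatigue and Grade 3 neutropenia without fever have the same 7-day threshold.
- *Missed Day 15 infusion.* The immune-related guidance in 5.5.2.4 generally holds treatment for a Grade 2 event. If the hold carries past the Day 15 window, the second bullet is met. If the event then worsens to a DLT inside Cycle 1, the subject has already met a replacement criterion.
- *Death from a DLT in the window.* This subject cannot complete follow-up, so the 10.4.1 definition is not met.

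**Effect on the decision.** Let p be the true DLT rate and q the share of DLT subjects dropped and replaced. Both are assumptions; the documents give neither.

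- P(accept) = P(0 or 1 of 6) + P(2 of 6) × P(0 of 3)
- Apparent rate after dropping = p(1 − q) / (1 − pq)

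At p = 0.40:

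- q = 0: 0.2333 + 0.3110 × 0.2160 = 0.300
- q = 0.25: apparent rate 0.30/0.90 = 0.333; 0.3512 + 0.3292 × 0.2963 = 0.449
- q = 0.50: apparent rate 0.20/0.80 = 0.250; 0.5339 + 0.2966 × 0.4219 = 0.659

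Probability of accepting the dose:

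| True DLT rate | None dropped | Quarter dropped | Half dropped |
|---|---|---|---|
| 20% | 0.781 | 0.870 | 0.944 |
| 33.3% | 0.449 | 0.601 | 0.781 |
| 40% | 0.300 | 0.449 | 0.659 |
| 50% | 0.139 | 0.246 | 0.449 |

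**DLT definition.** SAP 1.1 gives the general rule (Grade 3 or higher non-hematologic, Grade 4 hematologic) without the clarifications in Protocol 5.3. Read alone, it would miss Grade 3 neutropenia with fever, which 5.3 lists, and would count brief Grade 3 vomiting, which 5.3 qualifies by duration. The net direction is mixed.

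**The case against.** The strongest reply is that the plan already protects DLTs. The third bullet and the synopsis both replace only subjects who stop for reasons other than a DLT. The missed-dose bullets appear to describe other people: "Subjects who are replaced for missed doses may continue to receive study treatment if there is a clinical benefit", whereas a DLT subject must stop. Protocol 5.2 counts DLTs observed in the cohort, the Dose Level Review Committee reviews each cohort's safety data, and neither refers to the SAP set. Adverse events in replaced subjects are still reported in the Safety Population. Stopping drug does not end safety follow-up either, since adverse events are collected for 30 days after ibrutinib and 90 days after MEDI4736.

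Most of this stands, and it defeats a stronger reading that a reader might infer: that every dose not taken after a DLT counts as missed. On that reading a last ibrutinib dose by Day 23 leaves 28 − 23 = 5 doses untaken. With onset uniform over 28 days, 23/28 = 82% of DLTs would be dropped, and acceptance at a 33% true rate would rise from 46% to 98%. The documents do not support this. It would empty the third bullet's exemption of nearly all effect, and they give no onset distribution.

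The reply does not close the three routes above. In the first two, a replacement criterion can be met before the event is a DLT; in the third, follow-up cannot be completed. Nothing in 5.2 or the committee's remit says whether a replaced subject's DLT counts. The SAP 1.1 wording is a summary, and SAP section 5 does not list the DLT definition as a change, so Protocol 5.3 presumably governs. That is a lesser point.

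**Conclusion.** The gap is real but narrow. Intent is clear for subjects taken off drug because of a recognised DLT, and those should be retained. What is missing is a rule that settles DLTs that qualify late, follow a missed infusion, or end in death before the window closes. For these, the written definitions allow replacement and exclusion, always in the direction of accepting the dose.

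The size cannot be fixed from the documents. At an assumed 40% true rate, acceptance is 30% if nothing is lost, about 45% if a quarter of DLT subjects are lost and 66% if half are. This assumes independent subjects, replacement from the same population, and that a replaced subject's DLT is not counted. If the exemption is applied to every DLT, the loss is zero. The figures show how sensitive the rule is; they do not predict what the trial would do.

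**What to change.** - In Protocol 5.3 and 10.4.1 and in SAP 2.1, state that any subject with a DLT in the observation period is DLT-evaluable and counted, whatever doses were missed and whether or not follow-up was completed. Add that the missed-dose replacement bullets apply only to subjects without a DLT.
- In SAP 2.1, replace the reference to section 1.4.1 with Protocol 5.3.
- In SAP 1.1, refer to the Protocol 5.3 DLT definition with its clarifications, so that the two passages are reconciled.

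Do not go further and limit the missed-dose bullets to misses that were not caused by treatment-related toxicity. That would keep under-exposed subjects without a DLT in the denominator as non-DLTs, which lowers the observed rate and brings back the same bias.

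The cost is a few sentences in two documents. The 6+3 rule and the range of 6 to 36 evaluable subjects do not change.

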2.2. Definition of Subgroups

Subgroup	Definition of subgroup	Type of Analysis
PD-L1 Expression	High versus Low/None	D, E (ORR)
Histology for NSCLC cohort	adenocarcinoma versus squamous-cell carcinoma	D, E (ORR)
Histology for Breast Cancer cohort	HER2-positive versus triple-negative	D, E (ORR)

D: Demographics and baseline disease characteristics. E: Efficacy. ORR: Overall response rate.

3. SUBJECT INFORMATION

3.1. Subject Disposition

Subject disposition will be summarized by each tumor type cohort. Subject enrollment will be summarized by region, country, and investigator.

Time on study is defined in the same way as overall survival with reversed censoring, i.e., subjects who died will be censored at death date. The Kaplan-Meier method will be used to estimate the median time on study.

3.2. Demographics and Baseline Characteristics

Baseline characteristics and demographic information at baseline will be summarized with descriptive statistics by tumor type cohort.

3.3. Prior and Concomitant Medications

Medications will be coded to a generic name and an Anatomical Therapeutic Chemical (ATC) class per the World Health Organization (WHO) drug dictionary. Concomitant medications will be summarized by therapeutic class and preferred term and by tumor type cohort. Concomitant medications are defined as medications that were taken at any time on treatment (i.e. from the date of the first dose of study treatment through the date of the last dose of study treatment). The following concomitant medications will be summarized separately: growth factors, blood supportive products and immunoglobulin, CYP3A inhibitors/inducers, anticoagulants and/or antiplatelets.

3.4. Extent of Exposure to Study Treatment

Exposure to study treatment will be summarized by tumor type cohort. Descriptive statistics will be provided for treatment duration and dosing information (e.g. total cumulative dose administered, relative dose intensity, dose reduction due to adverse events) for all study treatments.

3.5. Previous Treatment History and Subsequent Antineoplastic Therapies

Previous treatment history and subsequent antineoplastic agents will be summarized separately.

4. EFFICACY AND SAFETY ANALYSES

4.1. Efficacy Analyses

Efficacy endpoints and analysis methods are summarized in Table 2.

Table 2: Summary of Efficacy Analyses

Endpoint	Definition	Analysis Methods
Primary Endpoint		
Overall Response Rate (ORR)	Proportion of subjects achieving the best overall responses of CR or PR with confirmation	
Primary (Response-evaluable population)
 
 Proportion and 2-sided 95% CI based on exact Binomial distribution (Clopper-Pearson) Waterfall plot on tumor load from target lesion 
Sensitivity (Treated population)
 
Proportion and 2-sided 95% CI based on exact Binomial distribution (Clopper-Pearson)
 
Subgroup (Response-evaluable population)
 
 PD-L1: High vs. Low/None (all cohorts) Histology (Breast Ca: HER2 positive vs. Triple negative; NSCLC: Adenocarcinoma vs. Squamous-cell Carcinoma)
Secondary Endpoints		
Disease Control Rate (DCR) at Cycle 5	Proportion of response-evaluable subjects who maintain disease control (CR, PR or SD) at Week 20 (Cycle 5)	
Primary (Response-evaluable population)
 
Proportion and 2-sided 95% CI based on exact Binomial distribution (Clopper-Pearson)
 
Sensitivity (Treated population)
 
Proportion and 2-sided 95% CI based on exact Binomial distribution (Clopper-Pearson)

Duration of Response (DOR)	Duration of time from the date of initial response to the date of disease progression or the date of death due to any cause, whichever occurs first	
Primary (Response-evaluable population)
 
Proportion and Kaplan-Meier estimate
 
Sensitivity (Response-evaluable population)
 
Proportion and Kaplan-Meier estimate for confirmed and unconfirmed response

Progression Free Survival (PFS)	Duration of time from the first dose date of study treatment (ibrutinib or durvalumab) to the first documentation of disease	
Primary (Treated population)
 
 All PD and death considered events regardless any anticancer therapy prior to PD Kaplan-Meier curve

Endpoint	Definition	Analysis Methods
	progression or the date of death due to any cause, whichever occurs first	Sensitivity (Treated population) 
 • Subjects are censored for use of subsequent anticancer therapy prior to PD or death; subjects are censored after missing two or more consecutive assessment prior to PD or death • Kaplan-Meier curve
Overall Survival (OS)	Duration of time from the first dose date of study treatment (ibrutinib or durvalumab) to the date of death due to any cause	Primary (Treated population) 
 • All death considered events regardless of any anticancer therapy prior to death • Kaplan-Meier curve

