##### **10.6.2.1. Primary Efficacy Analysis**

The primary efficacy analysis will be based on ORR using the Response-evaluable Population in each of the three solid tumor cohorts. ORR is the proportion of response-evaluable subjects who achieved a CR or a PR with confirmation. The observed ORR along with its 95% confidence interval based on exact binomial distribution will be calculated and summarized for each tumor cohort.

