1.3. Statistical Hypotheses

There is no hypothesis testing for Phase 1b. The primary objective of Phase 2 is to evaluate overall response rate (ORR) for the combination therapy at RP2D. Hypothesis testing will be conducted to address this objective as follows:

Null hypothesis (H_0): $P \leq x\%$; where P denotes overall response rate.

Alternative hypothesis (H_a): $P > y\%$; where P denotes overall response rate.

For NSCLC cohort and breast cancer cohort, a true response rate of 10% (H_0) versus 25% (H_a) will be tested. For pancreatic cancer cohort, a true response rate of 5% (H_0) versus 18% (H_a) will be tested.

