1.4. Sample Size Determination

The study is not powered for comparison of dose cohorts or tumor type cohorts.

Phase 1b: Dose de-escalation will follow the 6+3 design and up to four dose cohorts will be enrolled for the DLT to determine the RP2D for the combination therapy. Therefore, Phase 1b will enroll a minimum of 6 and a maximum of 36 evaluable subjects.

Phase 2: Hypothesis for the true response rate will be tested as described below independently for each tumor type cohort based on the statistical framework of Simon's optimal 2-stage design. With a 1-sided error rate of 0.05, each tumor type cohort would have 80% power based on the true response rate in the alternative hypothesis. Approximately 130 subjects (including the subjects treated at the RP2D in Phase 1b and with the tumor type) across the three tumor type cohorts will be included in the Phase 2 analyses.

NSCLC cohort and breast cancer cohort (n=18 for interim and n=43 for final per cohort):

For each of the two tumor type cohorts, a true response rate of 10% (H_0) versus 25% (H_a) will be tested and the probability of early stopping is at least 73.4% if the true response rate is $\leq 10\%$ (H_0), and no greater than 13.5% if the true response rate is $\geq 25\%$ (H_a).

An interim analysis (for futility) will be performed based on the first 18 evaluable subjects for each cohort independently. If 2 or fewer responders are observed among the 18 evaluable subjects in a cohort, the enrollment may be stopped. Otherwise, the cohort will continue to enroll an additional 25 evaluable subjects for a total of 43 evaluable subjects for the final analysis. The null hypothesis will be rejected if 8 or more responders are observed among the 43 evaluable subjects.

Each cohort will enroll subjects according to the histology ratio described in Section 1.1.

Pancreatic cancer cohort (n=17 for interim and n=44 for final):

A true response rate of 5% (H_0) versus 18% (H_a) will be tested and the probability of early stopping is at least 79.2% if the true response rate is $\leq 5\%$ (H_0), and no greater than 16.2% if the true response rate is $\geq 18\%$ (H_a).

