1.6. Testing Procedure and Level of Significance

The 2-sided significance level for the final analysis of primary endpoint (ORR) will be 0.05. Analyses of secondary endpoints will be performed using the same significance level.

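### At the smallest rejecting responder count in each cohort, the plan rejects H0 while its only planned ORR interval still contains H0, because neither the confidence level nor the method of the interval matches the test.

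*SAP*

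**What the plan says.** The design sections and the analysis sections describe the primary endpoint differently.

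- **Test.** SAP 1.4 tests the response rate "independently for each tumor type cohort based on the statistical framework of Simon's optimal 2-stage design" and adds: "With a 1-sided error rate of 0.05, each tumor type cohort would have 80% power". H0 is rejected at 8 or more responders of 43 in NSCLC and in breast cancer, and at 5 or more of 44 in pancreatic cancer. Protocol 10.4.2 has the same counts and the same 1-sided level.
- **Rates.** SAP 1.3: "For NSCLC cohort and breast cancer cohort, a true response rate of 10% (H_0) versus 25% (H_a) will be tested", and "For pancreatic cancer cohort, a true response rate of 5% (H_0) versus 18% (H_a) will be tested".
- **Futility stop.** It is worded as an option. SAP 1.4: "If 2 or fewer responders are observed among the 18 evaluable subjects in a cohort, the enrollment may be stopped". For pancreas the boundary is 1 or none of 17. SAP 1.1 lets biomarker findings or tumour shrinkage justify going on.
- **Level.** SAP 1.6: "The 2-sided significance level for the final analysis of primary endpoint (ORR) will be 0.05".
- **Estimate and interval.** Protocol 10.6.2.1: "The observed ORR along with its 95% confidence interval based on exact binomial distribution will be calculated". SAP 4.1, Table 2, specifies "Proportion and 2-sided 95% CI based on exact Binomial distribution (Clopper-Pearson") on the Response-evaluable Population and repeats it on the Treated Population as sensitivity.

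Neither document gives a two-stage interval, p-value or estimate. Neither says what to report if the count and the interval disagree.

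**The concern.** A two-sided 95% interval corresponds to a 1-sided 0.025 test, whereas the responder counts were chosen for 1-sided 0.05. Clopper-Pearson also treats 43 or 44 subjects as one fixed sample, whereas the counts hold their level only because some cohorts stop at 18 or 17. The interval therefore differs from the test in two ways.

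At stake is a primary result that can be read two ways. A cohort that ends on its minimum rejecting count would be reported as rejecting H0 beside an interval that includes H0. SAP 1.6 would give a reader grounds to call the same cohort negative. Settling that after the data are seen would be a post-hoc choice on the primary endpoint.

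**Working it through.** **Inputs.** NSCLC and breast: p0 = 10%, p1 = 25%, stop at r1 = 2 or fewer of n1 = 18, reject at s = 8 or more of n = 43. Pancreas: p0 = 5%, p1 = 18%, stop at r1 = 1 or fewer of n1 = 17, reject at s = 5 or more of n = 44. All are from SAP 1.3 and 1.4. The two-stage sums assume that the stop is followed and that a response is defined the same way at both stages.

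**1. The plan's own figures.** Let X ~ Bin(n1, p) and Y ~ Bin(n - n1, p). Early stopping is P(X ≤ r1). Rejection is R(p; s) = sum over x > r1 of P(X = x) · P(Y ≥ s - x).

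| | early stop under H0 / Ha | alpha | power |
|---|---|---|---|
| NSCLC, breast | 73.4% / 13.5% | 0.0480 | 80.0% |
| Pancreas | 79.2% / 16.2% | 0.0469 | 80.4% |

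These match the stated stopping probabilities and power, and a search for Simon's optimal design returns the same boundaries. If the stop is never applied, alpha is P(Bin(43, 0.10) ≥ 8) = 0.061 and P(Bin(44, 0.05) ≥ 5) = 0.067. The level therefore depends on the stop.

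**2. Intervals at the cut-offs.** The Clopper-Pearson lower limit solves P(Bin(n, p) ≥ s) = a/2. The two-stage interval, which orders outcomes by stage and then by responses, has lower limit R(p; s) = a/2 and upper limit P(stop at stage 1, or reach stage 2 with S ≤ s) = a/2. Here S is the total number of responders, and a is 0.05 or 0.10.

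| | 8/43 (H0 10%) | 5/44 (H0 5%) |
|---|---|---|
| Clopper-Pearson 95% (planned) | 8.4-33.4%, contains | 3.8-24.6%, contains |
| Clopper-Pearson 90% | 9.6-31.1%, contains | 4.6-22.4%, contains |
| Two-stage 95% | 8.8-36.3%, contains | 4.2-29.3%, contains |
| Two-stage 90% | 10.1-33.3%, excludes | 5.1-26.1%, excludes |

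Changing the level alone does not produce agreement, and neither does changing the method alone. Changing both does.

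**3. One responder more.** The planned 95% lower limit is 10.04% at 9/43 and 5.17% at 6/44, so the disagreement is confined to one count per cohort.

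**4. If the interval or the 2-sided level decided.** The cut-offs would become 9/43 and 6/44. The two-stage one-sided p-values at 8/43 and 5/44 are 0.0480 and 0.0469, above 0.025. At 9/43 and 6/44 they are 0.021 and 0.017, below it. The chance of ending exactly on 8/43 at 25% is 7.0%, and on 5/44 at 18% it is 5.8%. Power falls to 80.0 - 7.0 = 73.0% and 80.4 - 5.8 = 74.6%.

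**5. Bias of the observed proportion.** E = sum over x ≤ r1 of (x/n1) · P(X = x), plus sum over s of (s/n) · P(reach stage 2, S = s). The bias is -1.5, -2.0 and -1.2 points at true rates of 10, 17.5 and 25%, and -1.1, -1.8 and -1.3 points at 5, 11.5 and 18%. If every cohort runs to full size it is zero.

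**6. Coverage.** Over the two-stage sample space, the planned 95% interval covers the true rate with probability of about 98 to 99% at the rates examined.

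**The case against.** The strongest reply is that the decision rule is already explicit. SAP 1.4 and Protocol 10.4.2 reject on a count, and neither Table 2 nor Protocol 10.6.2.1 makes the interval the test. The overlap affects one count per cohort. The chance of landing there is 2.7% and 7.0% at 10% and 25% (NSCLC, breast), and 3.0% and 5.8% at 5% and 18% (pancreas). This limits how often the problem arises but does not remove it. SAP 1.6 supplies a competing level for the same endpoint. At intermediate activity the boundary count is also less rare: 9.4% at a true 15%, and 11.6% at a true 10% in pancreas.

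A reader might go further and infer three things that the documents do not support.

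- *That ignoring the two stages is, by itself, why the interval contains H0.* A correct two-stage 95% interval contains it too, so the conflict between 1-sided and 2-sided 0.05 is an equal part of the cause.
- *That the planned interval is invalid.* It is conservative.
- *That the headline ORR is materially biased.* The bias is 1 to 2 points, against intervals 20 to 25 points wide, and it arises only if a discretionary stop is followed.

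It can also be objected that a two-stage interval is not exact in this trial. That stands. The interim counts unconfirmed responses (SAP 1.5.2), while Table 2 counts confirmed ones. Enrollment continues during the interim (SAP 1.1), so the evaluable number may differ from the plan. The interval would have to be labelled approximate.

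The objection to requiring an unbiased estimate also stands. The uniformly minimum variance unbiased estimate averages 19.5% and 13.5% in cohorts that reach stage 2 under H0, against 14.0% and 8.3% for the observed proportion. It would also turn 3/43 into 16.7%.

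**Conclusion.** The point holds as a mismatch between the test, the stated level and the only planned interval. It is visible at exactly 8/43 and 5/44. The consequence is a contradictory primary result at those counts, or a loss of about 7 and 6 points of power if the interval or the 2-sided level is taken as the criterion. Level and method act together, and correcting either one alone leaves the contradiction in place. The point does not show that the Clopper-Pearson interval is invalid or that the observed ORR misleads by more than about 2 points.

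The two-stage figures assume that the stop is followed, the same response definition applies at both stages, and there are exactly 18 then 43, or 17 then 44, evaluable subjects. This should be settled before the analysis but does not threaten the design.

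**What to change.** - **SAP 1.6.** Replace the 2-sided 0.05 level for ORR with the 1-sided 0.05 of section 1.4, and state that the responder-count rule decides. The sentence that ties the secondary endpoints to the same level then needs its own wording.
- **SAP Table 2.** Add a two-sided 90% interval, ordered by stage and then by responses, as the interval that matches the test. Keep the observed proportion with 95% Clopper-Pearson, labelled descriptive.
- **Cohort continued past its futility boundary.** Report the fixed-sample interval for that cohort and say that the count rule then has alpha of about 0.061 (NSCLC, breast) or 0.067 (pancreas).
- **Limits of the interval.** Say that it is approximate, because interim responses are unconfirmed, final ones are confirmed, and the evaluable number may not equal the planned one.

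A uniformly minimum variance unbiased estimate may be added but is not needed. The cost is SAP wording and a short program. Conduct and sample size do not change. The downside is one more interval to explain.
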